9.2. Other Safety Assessments

9.2.1. SOWS

The SOWS is a self-administered scale for grading opioid withdrawal symptoms. It contains 16 symptoms whose intensity the patient classifies as: 0=“not at all”, 1=“a little”, 2=“moderately”, 3=“quite a bit”, and 4=“extremely”. In this study, patients will complete the SOWS daily, starting at the TV14, End of Treatment visit through to the Washout and Safety Follow-up Period visit. The SOWS will also be completed at the Premature Discontinue of Study Drug Treatment visit. As with all patients who are discontinued from study drug, the patient will complete a daily SOWS scale for the two weeks following the last dose of study drug (unless consent is withdrawn).

To evaluate the daily changes in the SOWS during the Washout Period after cessation of treatment, each of the 16 symptom items will be summarized for each of the first 14 days beginning with the End of Treatment visit as frequencies and percentages of patients. No formal analysis will be undertaken. Additionally, the sum of all non-missing responses for the 16 items (SOWS total score) will be derived and similarly presented for each of those 14 days.

The change from the End of Treatment visit (defined as the maximum SOWS total score across days from the End of Treatment visit date to 7 days following the End of Treatment visit date), to the Washout and Safety Follow-up visit (defined as the SOWS total score on the date of the Washout and Safety Follow-up Period or the latest date following the End of Treatment Visit and before the Washout and Safety Follow-up visit) will be summarized using descriptive statistics for each treatment group.

A categorical summary will also be provided for the number and percentage of patients by their highest observed SOWS total score during the 14-day (washout) period already defined. The categories will be: ≤ 10 , 11-20, 21-30, 31-40, 41-50, 51-60, >60 . No formal analysis will be undertaken.

Maximum SOWS symptom score (defined for each patient for each day of the Washout and Safety Follow-up Period as the maximum (i.e. worst) non-missing score across all 16 symptom items) will be summarized using descriptive statistics for each treatment group.

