2.2. Secondary Objectives

The secondary objectives of the study are:

- To evaluate the safety of nalbuphine by achieved maintenance dose at the end of Treatment Week 4,
- To assess skin lesion improvement using the metrics of the Prurigo Activity Score (PAS),
- Change from Baseline in Patient-Reported Outcome (PRO) measures Worst (i.e. most severe itching over the past 24 hours) itch Numerical Rating Scale (NRS), average itch intensity NRS, Verbal Rating Scale (VRS) (itchy, burning and stinging), Medical Outcomes Scale (MOS) Sleep-R, ItchyQol, and Hospital Anxiety and Depression Score (HADS) by the final Treatment Period Visit,
- Change between Baseline and the final Treatment Period Visit in Patient Benefit Index, pruritus version (PBI-P),
- A description of the percentage of patients utilizing various doses of nalbuphine HCl ER tablets by Study Week,
- A description of the frequency and reasons for dose up-and down-titration and treatment discontinuation during the study,

- Frequency and distribution by time on study of patients determined to meet failure-to-improve criteria,
- Changes in the PRO measurements during the Washout Period after cessation of treatment of nalbuphine HCl ER tablets,
- Time to first use of rescue medications and the number of days of use of rescue medications for itching,
- To evaluate the daily changes in the Subjective Opiate Withdrawal Scale (SOWS) during the Washout Period after cessation of treatment of nalbuphine HCl ER tablets.

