The total amount of time in the Observation Period cannot exceed 12 weeks. After these 12 extended screening weeks, patients not eligible for the Treatment Period are screen failed from the study. The study periods are summarized below.

Study Period	Study Weeks	Duration
Observation Period	
Patients who do not meet the criteria to start Treatment are followed in Observation Period visits (OV) for up to 12 extended screening weeks. During this time, the patient may meet criteria and become eligible to enter the Treatment Period. If the patient does not meet the criteria to enter the Treatment Period by the end of 12 extended screening weeks (OV12), participation in the study ends and the patient is screen failed
	Up to 12 Extended Screening weeks
Treatment Period	
For patients directly entering the Treatment Period as of Visit 1a, the Treatment Period begins with Study Week 1 (Visit 1a) and ends with Study Week 50.
 
For patients entering the Treatment Period after being followed in the Observation Period, the number of weeks on treatment and the end of the Treatment Period varies. (See Table 8 in the study protocol for the details of which treatment visits are to take place).
 
The End of Treatment Visit will take place after the patient completes the last week of study drug.
	Up to 50 weeks
Washout and Safety Follow-Up Period	
The Washout and Safety Follow-up Period is two (2) weeks in duration.
 
For patients directly entering the Treatment Period as of Visit 1a and completing 50 weeks of study drug treatment, the Washout and Safety Follow-up Period should take place during weeks 51 and 52.
 
For patients entering the Treatment Period after being followed in the Observation Period, the number of weeks on treatment and the end of the Treatment Period varies; Table 8 in the Study Protocol calculates the Treatment Visit assignments for any patient entering the Treatment Period from the respective Observation Period visits. The Washout and Safety Follow-up Period will take place during the two (2) weeks after the patient completes the last week of study drug.
 
The Washout and Safety Follow-up Period Visit will take place in the week following the completion of the two (2) week Washout and Safety Follow-up Period.
	2 weeks

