3.2.2. Premature Discontinuation of Study Drug Treatment For Reasons Other Than Failure-to-Improve

Patients who complete Study Drug treatment through the End of Treatment Visit 14 (TV14) (even if some doses have been missed or if the patient was followed in the Observation Period before receiving study drug treatment) are considered to have completed Study Drug treatment. Patients discontinuing Study Drug treatment prior to the maximum allowable number of Treatment Weeks (based on their entry into the study at either Visit 1a or Visit 1b) will also be considered to have prematurely discontinued Study Drug treatment. Patients discontinuing Study Drug treatment prior to End of Treatment Visit 14 will be considered to have prematurely discontinued Study Drug treatment and will be asked to complete the End of Treatment Visit (TV14) regardless of where they were in the study visit schedule, the Washout and Safety Follow-up Period Visit and the Premature Discontinuation of Study Drug Telephone Contact visit. Patients removed from the study after enrollment and who have received a dose of study drug will not be replaced.

Some reasons for premature discontinuation of Study Drug treatment include:

- Intercurrent illness
- Any intolerable Adverse Event (AE) that cannot be ameliorated or safely managed with medical intervention or one that poses undue risk to the subject if Study Drug treatment were continued in the opinion of the Medical Monitor or Investigator
- Electrocardiogram (ECG) changes summarized in protocol Section 17.4
- Opioid medication is introduced in anticipation for chronic use of greater than 2 weeks
- Any medication prescribed for chronic anti-pruritic use of greater than 2 weeks
- Development of substance abuse as determined by the Investigator.

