3.3.2. Secondary Endpoints

Visit 1a or Visit 1b will serve as the baseline visit for efficacy endpoints. Visit 1a will be the Baseline for patients directly entering the Treatment Period as of Visit 1a. Visit 1b will be the Baseline for patients entering the Treatment Period after participating in the Observation Period for any length of time.

The secondary endpoints are:

- Assess skin lesion improvement using the metrics of the PAS
- Change from Baseline in PRO measures Worst itch NRS, average itch intensity NRS, VRS (itchy, burning and stinging), MOS-Sleep-R, ItchyQoL, HADS by Treatment Period study visit and Baseline NRS score
- Change between Baseline and the final Treatment Period visit in PBI-P
- A description of the percentage of patients utilizing various doses of nalbuphine HCl ER tablets by study week
- A description of the frequency and reasons for dose up-and down-titration and treatment discontinuation during the study
- Frequency and distribution by time on study of patients determined to meet failure-to-improve criterion
- Changes in the PRO measurements during the Washout Period after cessation of treatment of nalbuphine HCl ER tablets
- Time to first use of rescue medications and the number of days of use of rescue medications for itching
- To evaluate the daily changes in the SOWS during the Washout Period after cessation of treatment of nalbuphine HCl ER tablets.

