8.6. Premature Discontinuation Due to Lack of Efficacy or Adverse Events

The distribution of patients who prematurely discontinue due to lack of efficacy or adverse events during the Treatment Period and Washout Period will be summarized for the safety population across all Treatment Period visits, separately at each Treatment Period visit, and for the Washout Period. Date of discontinuation during the Treatment Period will be defined as the date of last dose of study medication. For patients who complete the Treatment Period, date of discontinuation during the Washout Period will be defined as the earliest non-missing of the date of last contact or the last observed visit date.

9. Safety Analysis

All analyses of safety will be conducted using the safety population.

No formal statistical analysis will be performed on safety outcomes; inferences, if any, will be derived through clinical review and interpretation.

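### SOWS summaries count days from the End of Treatment visit, not the last dose, so patients who stop between visits are shown on the wrong off-drug day

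*SAP*

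**What the plan says.** The secondary objective in SAP Section 2.2 is "To evaluate the daily changes in the Subjective Opiate Withdrawal Scale (SOWS) during the Washout Period after cessation of treatment", and Section 3.3.2 repeats it as an endpoint. Time since stopping drug is therefore the intended axis.

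Section 9.2.1 gives two collection rules. The general one is that "patients will complete the SOWS daily, starting at the TV14, End of Treatment visit through to the Washout and Safety Follow-up Period visit". For patients discontinued from study drug, "the patient will complete a daily SOWS scale for the two weeks following the last dose of study drug". The section adds a SOWS at the premature discontinuation visit, which does not settle which rule sets the start of the daily diary.

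For analysis, "each of the 16 symptom items will be summarized for each of the first 14 days beginning with the End of Treatment visit", and the daily total score uses the same 14 days. The highest-score categories refer back to that 14-day period. The End of Treatment value is the maximum total score from the visit date to 7 days later. The daily maximum symptom score is the exception: it is defined by day of the Washout and Safety Follow-up Period.

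On the timing of the visit, Section 3.1 says: "The End of Treatment Visit will take place after the patient completes the last week of study drug". Under Section 3.2.2, early stoppers "will be asked to complete the End of Treatment Visit (TV14) regardless of where they were in the study visit schedule".

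**The concern.** Collection for discontinued patients runs from the last dose, while tabulation runs from a visit, and nothing in the SAP re-aligns the two. Someone who stops at home between visits, for example because of an adverse event, may attend the End of Treatment visit some days later. That person's table day 1 is a later off-drug day than table day 1 for a patient seen at once.

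Two things are at stake. Each day column can pool patients at different times off drug, so the display no longer shows a course by time since cessation. And symptoms in the days between last dose and visit cannot contribute to the highest-score categories. Safety and tolerability is the primary objective of this open-label extension, and the daily SOWS is its direct description of withdrawal.

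**Working it through.** The SAP states no figure on this point, so there is none to reproduce. The check is a day count.

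**Inputs**
- Table window: 14 days, day 1 being the End of Treatment visit (Section 9.2.1).
- Diary for discontinued patients: two weeks after the last dose, taken as off-drug days 1 to 14 with the last-dose date as day 0 (Section 9.2.1).
- End of Treatment maximum: visit date to 7 days later (Section 9.2.1).
- Gap L from last dose to visit: not stated. Section 3.2.2 gives no maximum and Section 4.2 defines no analysis visit windows. Values from 0 to 14 days are assumed.

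**Formulas**
- Table day k shows off-drug day L + k - 1, for k = 1 to 14.
- For L of 1 or more, off-drug days 1 to L - 1 fall before the table, so L - 1 of 14 days are missing.
- The 7-day maximum covers off-drug days L to L + 7.

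**Results**

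| Assumed L | Table day 1 is off-drug day | Off-drug days not in table | Share of 14 | 7-day maximum covers off-drug days |
|---|---|---|---|---|
| 0 | 0 | 1 (day 14) | 1/14 = 7% | 0-7 |
| 1 | 1 | 0 | 0% | 1-8 |
| 3 | 3 | 2 (days 1-2) | 2/14 = 14% | 3-10 |
| 7 | 7 | 6 (days 1-6) | 6/14 = 43% | 7-14 |
| 14 | 14 | 13 (days 1-13) | 13/14 = 93% | 14-21 |

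If the diary ends two weeks after the last dose, then for L of 2 or more the last L - 1 table columns have no planned entry for that patient.

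**Two readings of collection**
- Diary starts at last dose: entries for days 1 to L - 1 exist but are not tabulated.
- Diary starts at TV14: those entries were never made, and the tables do not show it.

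**Direction**
- Highest score: under the first reading, the window holds only part of the patient's entries since stopping. A maximum over part cannot exceed the maximum over all, so the category is equal or too low.
- 7-day maximum: its window is shifted (7-14 instead of 0-7 at L = 7), so arithmetic fixes no direction.
- Day columns: direction depends on the withdrawal time course, which the SAP does not give.

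**After the change**
With day = SOWS date minus last-dose date, column k is off-drug day k for every patient, whatever L is.

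**The case against.** The strongest objection is that the effect depends on a gap nobody can see. Visit timing belongs to the protocol, which is not at hand. For scheduled completers the visit follows the last dosing week, and for failure-to-improve stops the decision is made at a treatment visit (Section 3.2.1), so the shift is probably nil or one day. What remains is an unknown number of patients who stop between visits. This stands, and it limits the size of the point. It does not remove the mismatch, which is in the text of Section 9.2.1.

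A second objection is that if the diary starts only at TV14, re-anchoring recovers nothing. This also stands in part: the labels would be corrected, but missing days would stay missing. It is the reason to reconcile the two collection rules and to show how many patients have no early entry.

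Third, the proposed clock is not perfect. Section 7.3.2 substitutes the visit at which drug was last returned when the last-dose date on the completion page is missing or the patient is lost to follow-up. Those patients need a flag.

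Finally, the summaries are descriptive and SOWS is a secondary endpoint. True, so no error rate is at stake.

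**Conclusion.** The point holds as an inconsistency of time origin that should be corrected. It affects the item table, the daily total score, the 7-day maximum and the 14-day highest-score categories. At assumed gaps of 3, 7 and 14 days, 2, 6 and 13 of 14 off-drug days are missing from that patient's tables; with no gap or a one-day gap the effect is one day or nil. The number of patients affected cannot be derived from the SAP.

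A reader might infer more, and the SAP does not support it:
- That the loss is L/14, or 21%, 50% and 100% at these gaps. This counts the visit day as lost, although it is tabulated.
- That L days beyond the two weeks enter the table. They do so only if the diary continues that long; otherwise the cells are empty.
- That all daily percentages lean toward less withdrawal. Only the 14-day highest score has a known direction, and only if earlier entries exist. A patient seen late could score higher in column 1 than one seen on the last-dose day.
- That the effect falls mainly on patients who stopped for intolerance. The SAP has no data on this.
- That every daily SOWS summary is affected. The daily maximum symptom score is tied to the Washout Period, not explicitly to the visit.

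**What to change.** In Section 9.2.1:

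1. Define washout day = SOWS date minus date of last dose, using the Section 7.3.2 derivation, and flag patients whose last-dose date was replaced by a visit date. Section 8.6 already takes this origin: "Date of discontinuation during the Treatment Period will be defined as the date of last dose of study medication".
2. Use this day for the item table, the daily total score, the 7-day maximum and the highest-score categories. State that the daily maximum symptom score uses the same scale.
3. Show the number of patients with an entry on each day, and the number with none in the first days off drug.
4. Reconcile the two collection rules, stating whether discontinued patients start the daily diary at last dose or at TV14.

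The cost is a wording change and one derived variable from dates the SAP already expects: the last-dose date is on the eCRF. The small downside is fewer patients in the earliest day columns, which the counts will make visible. Days never collected cannot be recovered.

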8.1.4. Change from Baseline in the HADS

The HADS instrument includes 14 multiple-choice questions, each with 4 possible choices, scored between 0 and 3.

Separate anxiety and depression subscale scores will be derived, each with a possible value of 0-21 with higher scores indicating worse impairment.

The HADS anxiety subscale score will be derived as the sum of the responses to the following items:

- I feel tense or wound up
- I get a sort of frightened feeling as if something bad is about to happen
- Worrying thoughts go through my mind
- I can sit at ease and feel relaxed
- I get a sort of frightened feeling like butterflies in the stomach
- I feel restless and have to be on the move
- I get sudden feelings of panic.

The HADS depression subscale score will be derived as the sum of the responses to the following items:

- I still enjoy the things I used to enjoy
- I can laugh and see the funny side of things
- I feel cheerful
- I feel as if I am slowed down
- I have lost interest in my appearance
- I look forward with enjoyment to things
- I can enjoy a good book or radio or TV program.

In the event of a single missing item from a subscale, the missing value will be derived as the mean of the remaining six items. If more than one item is missing, then the subscale score will not be derived.

Summaries for the anxiety and depression scales will be will be presented as detailed in Section [8.1](#).

Responses to each of the 14 individual HADS items will be summarized at the baseline visit, Visit 14/End of Treatment visit and at the Washout and Safety Follow-up visit using descriptive statistics.

Individual HADS items and anxiety and depression subscale scores will be presented in a data listing for the safety population.

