8.1.5. Change from Baseline in the ItchyQoL

The ItchyQoL consists of 22 pruritus-specific items measuring how pruritus affects patients' QOL in the area of symptoms related to the itch condition (6 questions), functional limitations (7

questions), and emotions (9 questions). The subject scores each question never =1, rarely=2, sometimes=3, often=4 and all the time=5.

Individual scores for each of the 22 items will be summarized categorically using frequencies and percentages at each study visit.

The ItchyQoL total score will be obtained as the sum of the 22 items. If no more than three items are missing, each missing item will be estimated as the mean of the remaining items. If more than three items are missing, the ItchyQoL total score will be set to missing.

Summaries for ItchyQoL total score will be presented as detailed in Section [8.1](#). In addition, change in ItchyQoL total score between baseline and LOV will be summarized using frequencies and percentages for the following categories: very good improvement, marked improvement, some improvement, no change, slightly worse, markedly worse and much worse. The magnitude of ItchyQoL change associated with each category is taken from [Siebenhaar et al., 2013](#): Very good improvement: > 50% to 100% reduction; Marked improvement: > 20% to 50% reduction; Some improvement: > 5% to 20% reduction; No change: 5% reduction to 5% increase; Slightly worse: > 5% to 20% increase; Markedly worse: > 20% to 50% increase; Much worse: > 50% increase. The summary will be presented for all patients, patients with at least 6 months of treatment, patients with at least 9 months of treatment and patients who have completed the treatment period. Patients will be counted in each treatment duration category whose criteria they have met (i.e. A patient who has completed the treatment period will be included in the denominator for all patients, patients with at least 6 months of treatment, patients with at least 9 months of treatment and patients who have completed the treatment period.).

Individual ItchyQoL item scores as well as the calculated total score for each patient will be presented in a data listing for the safety population.

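### The SOWS total adds only the answered items with no completeness rule, so a blank item counts as an absent symptom; daily totals and peak bands can be too low, and the change score can err either way

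*SAP*

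**What the plan says.** SAP section 9.2.1 describes the SOWS as a self-administered withdrawal scale: "It contains 16 symptoms whose intensity the patient classifies as" 0 to 4, where 0 means that the symptom is absent. Patients complete it daily from the End of Treatment visit to the Washout and Safety Follow-up visit. The total is defined in one clause: "the sum of all non-missing responses for the 16 items (SOWS total score) will be derived". Nothing is said about how many items must be answered.

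Three outputs use that total:
- a daily display, "similarly presented for each of those 14 days";
- a change score whose starting value is "defined as the maximum SOWS total score across days from the End of Treatment visit date to 7 days following" that visit, compared with the score at the Washout visit or the latest earlier date;
- a table of patients "by their highest observed SOWS total score during the 14-day (washout) period already defined", in seven bands from ≤10 to >60.

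The SAP treats missing items differently on its other summed or averaged scales. For HADS (8.1.4): "In the event of a single missing item from a subscale, the missing value will be derived as the mean of the remaining six items"; with more missing, no subscale score is derived. For ItchyQoL (8.1.5), up to three missing items take the mean of the rest, and then: "If more than three items are missing, the ItchyQoL total score will be set to missing". For PBI-P (8.1.7), the score is the mean of the answered items. Section 4.7 says that missing data will not be imputed.

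**The concern.** On a scale whose lowest code is 0, a plain sum of the answered items is zero-filling under another name. A form with 3 of 16 items answered still yields a total, at most 3 × 4 = 12, and is tabulated beside complete forms with a range of 0 to 64. A reader of the tables cannot tell a low total that reflects few symptoms from one that reflects few answers.

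Daily SOWS change during washout is a named secondary objective and endpoint (2.2, 3.3.2) and a listed safety assessment (3.3.4), in a study whose primary objective is safety and tolerability. The tables are purely descriptive, so no error rate is at stake. But descriptive tables are all that the SAP plans for this scale, so the scoring rule determines what they show.

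**Working it through.** The SAP states no figure for this point, so there is none to reproduce. The check is arithmetic on the scoring rule.

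**Inputs (SAP 9.2.1).** 16 items, each 0 to 4, maximum 16 × 4 = 64. Bands: ≤10, 11-20, 21-30, 31-40, 41-50, 51-60, >60.

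**Step 1: equivalence.** Sum of answered items = sum over all 16 items with each blank set to 0. The recorded total therefore never exceeds the true total, and falls short of it by the summed true scores of the blank items.

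**Step 2: size on one form.** As an illustration, let all items share the same true level L, with m blanks. True total = 16L; recorded = (16 − m)L; relative shortfall = m/16. That is 6.25% for m = 1, 12.5% for 2, 18.75% for 3 and 25% for 4. With unequal levels, m/16 is only the expected shortfall if blanks fall at random across items.

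**Step 3: effect on bands.** Prorated total = 16 × (sum of answered items) / (number answered).
- L = 2, one blank: recorded 15 × 2 = 30 (band 21-30); true and prorated 32 (band 31-40).
- L = 3, three blanks: recorded 13 × 3 = 39 (band 31-40); true and prorated 48 (band 41-50).
- L = 4, one blank: recorded 15 × 4 = 60 (band 51-60); true and prorated 64 (band >60). With any blank item, the >60 band cannot be reached.
- Answered items summing to 20 are recorded in band 11-20. With 15 answered, proration gives 16 × 20/15 = 21.3; with 14, 16 × 20/14 = 22.9; with 13, 16 × 20/13 = 24.6. All three round into band 21-30.

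**Step 4: change score.** Take a true 32 at the peak and a true 32 at follow-up, so no change.
- Four blanks at follow-up, all items at 2: recorded 24, change 24 − 32 = −8, a false recovery.
- Four blanks on the peak day, with no other day in the window scoring higher: recorded maximum 24, change 32 − 24 = +8, a false worsening.

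The direction is therefore fixed for daily totals and highest-score bands, but not for the change score.

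**Step 5: comparison with the SAP's other scales.** HADS tolerates 1 missing of 7 (14.3%); ItchyQoL tolerates 3 of 22 (13.6%). On 16 items, 2 is 12.5% and 3 is 18.75%, so 2 is the closest match and 3 is somewhat more lenient.

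**The case against.** The strongest reply is that the effect may be small or nil. The SAP gives no item-missing rate. It does not say that the scale is completed at home or on paper, or that the form permits blanks; completeness checks may well sit in the protocol or the data capture system. The total is also not the only SOWS display. The 16 items are tabulated by day without zero-filling, and the daily worst-symptom score is wrong only if the worst item is the blank one. Withdrawal-suggestive adverse events are analysed separately (9.1.7). All of this stands, and it limits the size of the point. It does not supply the missing rule.

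A second reply is that proration has its own bias. It assumes that skipped symptoms resemble answered ones, and it overstates the total if patients skip symptoms that they do not have. This also stands, and is a reason to keep the tolerated number of blanks small.

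A third reply is that discarding incomplete days could itself hide withdrawal. If a patient's worst day has 12 items answered summing to 36, setting that total to missing would band the patient on a milder day, although 36 is a guaranteed lower bound. This is correct, and the fix has to protect such days.

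A reader might also infer that the rule always understates withdrawal in this trial. The document does not support that. Complete forms, and blanks for absent symptoms, carry no error; the 14-day maximum is unaffected when the blanks fall on a day that would not have been the peak; and the change score can move either way.

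**Conclusion.** The point holds as a defect in a stated scoring rule. Section 9.2.1 in effect scores blank SOWS items as absent symptoms, nothing elsewhere in the SAP corrects this, and the SAP handles missing items differently for HADS, ItchyQoL and PBI-P. Daily totals are too low whenever a blank symptom was present. A single blank can then move a patient down one band of the highest-score table if it falls on the peak day and no other day reaches the true band. The change score can err in either direction.

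The numerical examples assume either equal item levels or answered items that represent the blank ones. They show what the rule can do, not what it will do in these data. Because the item-missing rate is unknown, no overall size can be given, and the claim that withdrawal will be materially understated would go beyond the document. The point is worth correcting because it affects a named secondary and safety endpoint and the correction is cheap.

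**What to change.** Replace the clause in 9.2.1 with a completeness rule:
- If no more than a stated small number of items is missing on a day (for example 2 of 16, about the proportion tolerated for HADS and ItchyQoL, and at most 3), SOWS total = 16 × mean of the answered items, rounded to an integer for the banded table.
- If more items are missing, including a wholly blank form, which the SAP does not address, set that day's total to missing for the daily summaries and the change score.
- For the highest-score table, keep the raw sum of such a partly answered day as a lower bound when it exceeds the patient's highest evaluable total, so that a partly answered peak day is not lost.
- Report the number of incomplete forms by day.

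Align section 4.7 with this by excepting item-level scoring rules, which the HADS and ItchyQoL rules already need.

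The cost is a few sentences and a few lines of programming; results for complete forms do not change. Some incomplete days leave the daily total and change tables, and a lost day may be the peak that feeds the change score, so the count of incomplete forms should be read beside it. Proration may overstate the total if patients skip symptoms that they do not have.
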